5.7 PRE-MEDICATIONS AND MANAGEMENT OF INFUSION REACTIONS

Abbreviated Title: Early Initiation of Oral Therapy for Naïve Severe Aplastic Anemia (SAA)

Version Date: 11/05/2025

Subjects will receive pre-medication approximately 30 minutes prior to infusion of ATG as follows:

- oral diphenhydramine 1 - 1.5 mg/kg/dose (NTE 50 mg) administered orally or intravenously, and;
- oral acetaminophen 10-15 mg/kg/dose (NTE 650 mg)

Serum sickness prophylaxis with oral prednisone at 1 mg/kg/d will begin prior to the first dose of h-ATG, and will be continued for 10 days total and then tapered over the subsequent 7-14 days. Methylprednisolone at equivalent doses may be substituted for prednisone. Those subjects who develop serum sickness may require a longer tapering schedule and will be dosed individually as clinically indicated. Infusion reactions will be treated symptomatically (e.g., antiemetics, IV fluid hydration, acetaminophen, antihistamines, inhaled bronchodilators, meperidine). Prednisone dose will be calculated based on actual body weight.

In case of moderate or severe reactions hydrocortisone will be given and the infusion will be discontinued and restarted at a slower rate once the symptoms have subsided. If a subject has a persistent severe infusion reaction that does not respond to measures to ameliorate the signs/symptoms associated with the infusion, the h-ATG infusion will be discontinued (see section off study criteria) and subjects will go off study.

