9.6 OFF TREATMENT AND OFF STUDY CRITERIA

All subjects will go off study after 5-year NIH landmark visit.

Subject choice: Subjects may be removed from study at their request at any time. The risks of withdrawing will be discussed, as will alternative treatment options. The risks of withdrawing from the study including high mortality rate with supportive care only (if that is chosen) will be discussed in detail with the patient. Those subjects who choose to

Abbreviated Title: Early Initiation of Oral Therapy for Naïve Severe Aplastic Anemia (SAA)

Version Date: 11/05/2025

withdraw will be strongly encouraged to continue to have blood counts monitored until initiation of alternative SAA therapy or through the 6 months off study medication to assess for late occurring adverse events.

Principal investigator decision: Should any of the following events occur, study drug administration will be discontinued, and the subject will be followed until resolution of the event and labs will be monitored at least every week or as clinically indicated until he/she initiates alternative SAA therapy or through 6 months off study drug time point. Appropriate clinical experts such as ophthalmologist, etc. will be consulted as deemed necessary.

Adverse events related to:

- Death or any grade IV adverse event considered to be probably or definitely related to EPAG
- Life threatening acute hypersensitivity reactions
- Intolerance of eltrombopag not resolved by dose reduction
- Thrombosis/embolism (DVT, PE, stroke or TIA, myocardial infarction) other than line associated thrombosis
- Persistent hepatotoxicity as defined in section 6.4.2
- Infusion-related h-ATG reactions refractory to all appropriate supportive measures

Should any of the following events occur, study drug administration will be discontinued, and the subject will be taken off study.

Clonal evolution or relapse:

- Evidence of a poor risk clonal disorder (chromosome 7 abnormalities or complex cytogenetics) at any time while on study
- Evidence of myelodysplastic syndrome or AML according to WHO criteria at any time while on study
- Relapse criteria are met and treatment other than CsA and EPAG are started

Other

- Persistent non-compliance or lost to follow-up per PI discretion*
- Patients who require chemotherapeutic treatment or require drugs with hematological effects

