- Initiation of additional immunosuppressive therapy other than steroids or cyclosporine (if beyond 6 months then mycophenolate mofetil can also be administered per PI discretion in patients who cannot tolerate cyclosporine and who require immunosuppression) or if beyond 2 years, enroll in other available clinical trials.

Pregnancy: This protocol does not enroll patients who are pregnant or women of child-bearing potential unless they are using contraception during the study treatment period (Section 4.3).

Because aplastic anemia is a disease of young adults, if a woman becomes pregnant while participating in the study despite stringent contraception requirements and education by the study team regarding the risks of relapsed aplastic anemia with pregnancy upon study entry and at

Abbreviated Title: Early Initiation of Oral Therapy for Naïve Severe Aplastic Anemia (SAA)

Version Date: 11/05/2025

every landmark visit, patient may remain on study. This limited inclusion of pregnant women on this study permits capture of the secondary endpoint (relapse of aplastic anemia) without exposing the subject/fetus/neonate to study drugs or invasive protocol procedures.

- If a patient becomes pregnant while on study drugs (CSA and/or EPAG), patient will discontinue the medications immediately but may remain on study
- If a patient becomes pregnant during follow-up period and not on any study treatments, patient may remain on study
- No investigational interventions or research procedures will be performed during pregnancy (if landmark visit is due during pregnancy, it will be delayed till after). All clinical decisions about pregnancy management will be made by the patient and the treating physician.
- If a patient relapses with aplastic anemia during pregnancy, no treatment will be provided on study; recommendations will be provided to the local treating physician for clinical management and if pursued any treatment other than supportive care (transfusions), patient will be taken off study
- Blood count monitoring with complete blood counts (CBCs) will be obtained with increased frequency than otherwise indicated, especially in later gestation, to monitor for AA relapse
- Fetus/neonate is not a research subject in this protocol
- No inducements, monetary, or otherwise, will be offered to terminate a pregnancy
- Individuals engaged in the research will have no part in any decisions as to the timing, method, or procedures used to terminate a pregnancy.

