10.6 EVENT COLLECTION

10.6.1 Duration of Adverse Event Collection

The collection and recording of AEs will begin on the first day of initiation of the study drug and will continue for 30 days after the 6 month landmark visit or for 30 days after treatment is discontinued if before the 6 month landmark visit, after which the events will be captured in the medical record but not abstracted or recorded in the database. AEs that are abstracted in the database will be followed until satisfactory resolution.

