10.6.2 Duration of Serious Adverse Event Collection

The collection of SAEs will begin on the first day of initiation of the study drug and will continue as long as the subject is on study. Starting 30 days after the 6 month landmark visit or 30 days after treatment is discontinued (if before the 6 month landmark visit), SAEs will only be captured in the research database when deemed possibly, probably or definitely related to the study treatment.

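### Section 5.7 sends a subject with a refractory h-ATG infusion reaction off study, while section 9.6 lists that event for drug discontinuation and follow-up, so the disposition is inconsistent

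*Combined protocol and SAP*

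**What the plan says.** Section 5.7 deals with a severe h-ATG infusion reaction that persists despite treatment. Its instruction is that "the h-ATG infusion will be discontinued (see section off study criteria) and subjects will go off study". The cross-reference has no number, but 9.6 is the only section whose title covers off-study criteria.

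Section 9.6 has two lists with different consequences.

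- **First list (adverse events).** The heading says "study drug administration will be discontinued, and the subject will be followed until resolution of the event", with laboratory monitoring until alternative SAA therapy starts or the subject is 6 months off study drug. One entry is "Infusion-related h-ATG reactions refractory to all appropriate supportive measures".
- **Second list (clonal evolution or relapse, and other reasons).** The heading says "study drug administration will be discontinued, and the subject will be taken off study". h-ATG reactions are not on it. One entry that could apply later to the same subject is "Initiation of additional immunosuppressive therapy other than steroids or cyclosporine".

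Section 9.6 also sets a general end of participation: "All subjects will go off study after 5-year NIH landmark visit".

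**The concern.** The section that 5.7 cites does not contain the disposition that 5.7 gives. Staff who follow 5.7 end participation. Staff who follow 9.6 stop drug and keep following the subject. Two subjects with the same event could therefore be handled differently.

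The stake is follow-up. Section 9.2 plans up to 60 months so that long-term disease-free and overall survival can be estimated, and section 2.3.7 gives relapse and high-risk clonal evolution as the reason for the extension cohort. Taking a subject out because of a treatment toxicity gives up those outcomes for a reason linked to treatment. That fits poorly with the intention-to-treat principle in 9.4.

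The two sections also differ on what is stopped. In 5.7 it is the h-ATG infusion; in 9.6 it is study drug, unspecified.

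**Working it through.** The plan gives no figure on this point to reproduce. The check is a comparison of the texts, followed by a bound on how many subjects could be affected.

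**1. Disposition of the same event**

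| | Section 5.7 | Section 9.6 |
|---|---|---|
| Trigger | Severe h-ATG reaction persisting despite measures | h-ATG reaction refractory to supportive measures |
| What stops | h-ATG infusion | Study drug (not named) |
| Status | Off study | Followed to resolution; on-study status not stated |
| In the list headed by removal from study? | Not applicable | No |

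**2. Does being on the first 9.6 list imply leaving the study?** No. Thrombosis is on the same list, and section 5.5.1 says that after thrombosis EPAG stops while CsA and h-ATG go on. A subject still receiving protocol therapy has not left. The second heading also adds removal from study in words, which would be redundant if the first list already meant it.

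**3. What is lost if 5.7 is followed?**

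- *Acute reaction:* not lost. Under 10.6.1, AEs are collected for 30 days after discontinuation if that falls before the 6-month visit, and "AEs that are abstracted in the database will be followed until satisfactory resolution".
- *Later SAEs:* partly lost. Under 10.6.2, SAE collection "will continue as long as the subject is on study". Even on study, from 30 days after treatment is discontinued, if that is before the 6-month visit, the database takes only SAEs judged at least possibly related. Under 10.7.4, later SAEs suspected to be related still go to the manufacturer.
- *Relapse, clonal evolution and survival:* lost from exit onward.
- *Primary endpoint:* not touched. Section 9.3 ends the study treatment period when standard treatment starts, which is before any h-ATG reaction.
- *Subjects given other immunosuppression:* they leave under 9.6 anyway, so for them the wording changes little.

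**4. How many subjects?** Section 9.3 puts 39 subjects as already accrued and 41 more to come. A change now can affect at most about n = 41 h-ATG courses, and fewer if h-ATG is omitted after complete response (section 3). The documents give no rate r for refractory reactions, so the values of r below are assumptions.

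Expected cases = n × r; chance of at least one = 1 − (1 − r)^n.

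| Assumed r | 41 × r | 1 − (1 − r)^41 |
|---|---|---|
| 0.5% | 0.21 | 18.6% |
| 1% | 0.41 | 33.8% |
| 2% | 0.82 | 56.3% |

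At r = 2%, the chances of 0, 1 and 2 cases are 0.98^41 = 0.437, 41 × 0.02 × 0.98^40 = 0.365 and 820 × 0.02² × 0.98^39 = 0.149. They sum to 0.951, so three or more cases have a chance of about 5%. More than one or two affected subjects is therefore unlikely over this range.

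**The case against.** The strongest reply is that both sections can be obeyed at once. The first list in 9.6 never says that the subject stays on study. Its monitoring is bounded, and the bound is almost the same as the one 9.6 uses for blood counts in subjects who choose to withdraw. One could stop the drug, monitor under 9.6 and still leave under 5.7, treating 5.7 as the event-specific rule. The first list also includes death, so it is not purely a list of people who remain on study. This stands in part. A reader might infer that 9.6 orders the opposite of 5.7, and the text does not support that. What remains is that 5.7 points to off-study criteria that do not list the event, and that 5.5.1 shows a first-list event need not end participation.

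A second reply concerns CsA and EPAG. A reader might infer that they ought to continue after an h-ATG reaction, because section 2.3.5 credits each with single-agent activity. The documents do not settle this. Elsewhere in 9.6, and in 10.7.5, the term study drugs refers to CsA and EPAG. On that usage 9.6 may mean that the oral drugs stop, and a default of continuing them could change the instruction. That is a clinical choice.

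A third reply is that the long-term loss exists only if 9.6 is read as keeping the subject on study, that subjects who leave may be consented to a standard-of-care protocol, and that data up to exit are kept. All of this is fair. But the standard-of-care protocol is not endpoint follow-up on this trial, and the 5-year exit in 9.6 makes continued participation the better reading.

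Finally, the rates used above are assumed. The nearest documented figure, anaphylaxis in fewer than 1% of patients (12.3.1), is a different event and gives no support to the 2% case.

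**Conclusion.** The inconsistency is real and is in current operative text, but minor. Section 5.7 orders exit; section 9.6, which it cites, lists the event for discontinuation and follow-up and leaves on-study status open. The reading that the subject remains on study is the better one, resting on the two separate headings, the 5-year default exit and the handling of thrombosis in 5.5.1. It is not stated.

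A reader might also infer that the acute reaction goes unrecorded or that the primary result is at risk. Neither follows: the reaction is captured on either reading, and the primary endpoint, sample size and error rates are unaffected. The loss is longer-term outcome data, mainly for subjects who do not start other immunosuppression. On the assumed rates the expected number is below one, and probably no more than one or two subjects would be involved, so the effect on secondary estimates is small.

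**What to change.** 1. **Section 5.7.** Replace the end of the sentence so that it reads, in substance: *h-ATG is stopped and the subject is followed per section 9.6*.
2. **Section 9.6, follow-up.** Add that for this event the subject stays on study for SAE, relapse, clonal-evolution and survival follow-up, unless another off-study criterion is met or consent is withdrawn.
3. **Section 9.6, drug.** Name the drug that stops, since 5.7 stops h-ATG while study drug in 9.6 can be read as CsA and EPAG. Whether those two continue is for the investigator to decide on clinical grounds and is not part of the required change.

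Moving the event to the second 9.6 list would also remove the mismatch, if the sponsor does intend exit, but it would give up outcomes that the extension cohort was added to measure.

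The cost is one sentence in 5.7, a short addition to 9.6, and follow-up visits up to 5 years for probably at most one or two subjects. Subjects given other immunosuppression would still leave under the existing rule.

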5.8 SUPPORTIVE CARE

- Transfusion support (blood and platelets) as clinically indicated.
- Hematopoietic growth factors (e.g., G-CSF, GM-CSF, or erythropoietin) if deemed necessary by the investigator or treating physician. Romiplostim (N-Plate) or IL-11 (Neumega) should not be administered.
- Estrogen, combination OCP's, or leuprolide as indicated for uterine bleeding (menses suppression).

5.10 INFECTION PROPHYLAXIS AND MONITORING

Pneumocystis jiroveci prophylaxis: During lower dose of CsA, routine *Pneumocystis jiroveci* prophylaxis (PJP) is not indicated. However, in patients with severe lymphopenia (Absolute lymphocyte counts <500/uL), PJP prophylaxis will be considered per PI discretion. It will be initiated upon starting h-ATG and higher dose of cyclosporine 3mg/kg q12h (6mg/kg q12h for pediatric) at the Clinical Center. Aerosolized pentamidine will be used as prophylaxis against *Pneumocystis jiroveci*, 300 mg approximately every 4 weeks by inhalation beginning the first month of higher cyclosporine therapy and to continue until month 6 when the cyclosporine dose is reduced.

Dapsone or another prophylactic regimen against *Pneumocystis jiroveci* may be substituted at the discretion of the PI. Bactrim (TMP/SULF) will be avoided because trimethoprim is a moderate to strong inhibitor of CYPs that may theoretically result in enhanced activity of EPAG. Children under 5 years of age (approximate) are often not able to complete the inhalation treatment with pentamidine and will receive dapsone or another prophylactic regimen at the discretion of the PI.

Antiviral prophylaxis: During lower dose of CsA, Valacyclovir is not indicated. However, in patients with severe lymphopenia (Absolute lymphocyte counts <500/uL), Valacyclovir prophylaxis will be considered per PI discretion. Valacyclovir, 500 mg once daily, will be administered for at least 1 month in all subjects regardless of HSV serology status at the time of h-ATG and higher dose cyclosporine at the Clinical Center. Pediatric subjects less than 40 kg will receive acyclovir (or equivalent) at 20mg/kg PO q12h to a maximum dose of 800mg q12h. Prophylaxis may be extended at the discretion of the PI.

Antibacterial and antifungal prophylaxis will not be included systematically with the immunosuppressive regimen but may be administered at the discretion of the PI or treating physician on a case-by-case basis.

5.11 INSTRUCTIONS TO SUBJECTS

Special instructions regarding CsA:

Regarding concomitant medications: Certain medications can change the level of cyclosporine in the blood. Some of these medications are erythromycin, ketoconazole, diltiazem, rifampin, phenytoin and phenobarbital. We will ask subjects to inform us of any medication taking concomitantly while on the study.

Regarding prohibited foods: Grapefruit and grapefruit juice may increase the effects of CsA by increasing the amount of this medicine in the body. Subjects will be advised not to eat grapefruit or drink grapefruit juice while taking this medicine.

Abbreviated Title: Early Initiation of Oral Therapy for Naïve Severe Aplastic Anemia (SAA)

Version Date: 11/05/2025

Regarding Immunizations: While taking CsA and for at least three months following discontinuation, immunizations should be avoided, and any planned immunization should be discussed with study investigators. There is almost no possibility that a vaccination given during this time period will be effective in stimulating immunity. Any live or attenuated vaccine may result in an infection, due to compromised immunity on CsA and h-ATG. Subjects should also avoid close household contact with individuals receiving the live oral polio vaccine for at least 72 hours following administration.

Special instructions regarding eltrombopag:

Timing in relation to food: Subjects will be advised to take EPAG on an empty stomach (1 hour before or 2 hours after a meal), or adhere to a restricted diet of low calcium (dairy products) and polyvalent cations at least 4 hours apart from co-administration of EPAG.

Timing in relation to antacids and polyvalent cations: Because co-administration of EPAG with antacids decreased plasma AUC of EPAG by 70%, subjects will be advised to take the EPAG at least 4 hours apart from antacids and other products containing polyvalent cations (i.e. aluminum, calcium, magnesium, iron, selenium and zinc) such as mineral supplements and dairy products.

5.12 Complications

Due to severely low blood counts in this disease process, there are several complications that may require urgent care/hospitalizations. Patients may receive this care at any hospital/facility that has capabilities of treating the presenting illness. Our research team will remain engaged in diagnostic/treatment decisions. Patients may be transferred to the Clinical Center if the treating hospital/facility lacks necessary treatment.

Common reasons for hospitalization in SAA patients may include bleeding, infections, and anemia related symptoms. Common reasons for hospitalization for the study treatment may include malignant hypertension/posterior reversible encephalopathy syndrome, hepatotoxicity, and acute renal failure.

6 CLINICAL MONITORING

Once patient has arrived at the Clinical Center, samples will be ordered and tracked through the CRIS Screens. Should a CRIS screen not be available, the NIH form 2803-1 will be completed and will accompany the specimen and be filed in the medical record.

6.1 PRE-STUDY EVALUATION/SCREENING

The following general screening procedures will be done either remotely during the initial telephone interview based on the labs done outside of NIH or at the NIH for those that are able to arrive at the NIH <72 hours.

- Medical history
- Physical examination (will be confirmed with the referring hematologist)
- Family history
- Concurrent medications

Abbreviated Title: Early Initiation of Oral Therapy for Naïve Severe Aplastic Anemia (SAA)

Version Date: 11/05/2025

PI may accept results from labs done outside of NIH as both screening and baseline as long as they are done within 30 days of enrollment, bone marrow aspirate/biopsy results will be accepted as long as it is performed within 90 days of enrollment:

- Complete blood count with differential
- Reticulocyte count
- Type and screen
- Acute care (Na, K, Cl, CO₂, creatinine, glucose, and urea nitrogen), Hepatic (Alk Phosphatase, ALT, AST, and Total Bilirubin), and lactate dehydrogenase. Direct bilirubin will be obtained per PI discretion if total bilirubin is elevated.
- Pregnancy test (urine or blood HCG in women of childbearing potential)
- Bone marrow aspiration and core biopsy stained for standard morphologic analysis and quantitation of cellularity with hematoxylin and eosin. Marrow sample will be reviewed here at the NIH with our pathologist.
- HIV serology (optional per PI discretion based on the clinical history)

Clinical studies to be performed at the Clinical Center on **first visit**:

- Complete blood count with differential and reticulocyte count
- Type and screen
- Acute care (Na, K, Cl, CO₂, creatinine, glucose, and urea nitrogen), Mineral (Phosphorus, Magnesium, Albumin, and Calcium), Hepatic (Alk Phosphatase, ALT, AST, Total Bilirubin), and Other (Total Protein, Uric Acid, and LDH). Direct bilirubin will be obtained per PI discretion if total bilirubin is elevated.
- Thyroid function tests, Folate, B12 level, iron panel (ferritin, transferrin, % saturation), DAT (direct antiglobulin test)
- Viral serologies for hepatitis A, B, C, HIV, HSV, EBV, and CMV (if not already available)
- PPD (at risk subjects only, based on history or geography) per PI discretion
- Flow cytometry of the peripheral blood to quantitate GPI-negative cells
- EBV and CMV PCR (if not already available)*
- HLA typing (if not already available)*
- Telomere length of leukocytes (if not already available)*
- Diepoxybutane (DEB) testing for Fanconi anemia per PI discretion (if not already available)*
- Lymphocyte peripheral blood phenotyping (analysis of T, B, and NK subsets via flow cytometry)*
- Bone marrow aspiration and core biopsy to be stained for standard morphologic analysis and quantitation of cellularity with hematoxylin and eosin, and special stains to assess reticulin and collagen, primitive stem and progenitor cells via CD34 immunohistochemistry, and other lineage-specific or special stains as indicated to classify any abnormalities**
- Bone marrow chromosomal analysis via standard cytogenetic techniques**
- EKG (to be done prior to h-ATG)
- Placement of a central line if subject does not have a pre-existing indwelling central venous catheter if treatment with h-ATG is indicated

- Chest X-ray - (not required to be performed, per PI discretion))

* Results if performed within the last 180 days either at NIH or outside NIH may be accepted. Only repeated if there are changes in the clinical status that may impact the results.

** At this visit, up to 30 mL total including the 15ml for exploratory/correlative research sample may be collected. For minors, the bone marrow biopsy & aspirate procedure will be done with general anesthesia.

6.2 ON STUDY OFF SITE MONITORING, PRIOR TO INITIAL CLINICAL CENTER VISIT IF ENROLLED ON STUDY REMOTELY

Prior to establishing care at the Clinical Center, patient will be followed closely by his/her local physician under complete guidance of the team at the Clinical Center (Appendix B). Weekly (+/- 3 days) telephone follow-up will be established with the patient. All the progress notes and labs indicated below will be requested to be sent from home physician to the research nurse. These documents will serve as source documents to collect data.

If a patient is unable to participate in a weekly follow up due to acute illness and hospitalization, the team will make contact with the treating physician and document patient's condition in lieu of a telephone follow up.

- Every 2-4 weeks – Progress note including history and physical examination by local physician
- Complete blood counts at least weekly (+/- 3 days), more frequent if clinically indicated. Frequency may be decreased to once every 2 weeks (+/- 4 days) per PI discretion. Only the following parameters will be recorded in the clinical database because of their relevance to the underlying disease and study treatment: absolute lymphocyte count (ALC) or lymphocyte percentage, absolute neutrophil count (ANC), or neutrophil percentage and white blood cell count if an absolute neutrophil count is not provided, hemoglobin, and platelets. Absolute reticulocyte count (or reticulocyte percentage and red blood cells [RBC] if an absolute reticulocyte count is not provided) will be recorded if available.
- Hepatic and renal panels (home panels must include hepatic transaminases, urea nitrogen (BUN), serum creatinine, and total bilirubin) at least weekly (+/- 3 days), more frequent if clinically indicated. Frequency may be decreased to once every 2 weeks (+/- 4 days) per PI discretion.
- Only the following parameters will be recorded in the clinical database because of their relevance to the underlying disease and study treatment: aspartate aminotransferase (AST), alanine aminotransferase (ALT), alkaline phosphatase (ALP), total bilirubin, creatinine, blood urea nitrogen (BUN), glucose, sodium, potassium, CO2 and chloride. Direct bilirubin will be obtained per PI discretion if total bilirubin is elevated.
- CsA blood level will only be obtained per PI/local physician discretion as clinically indicated. Due to low dose, there is no therapeutic target.

